13.5.2 Primary Efficacy Analysis

The primary efficacy endpoint, annualized rate of VOCs, will be analyzed using a stratified Wilcoxon rank-sum test based on stratification factors of region (North America/Europe vs. Africa/Middle East) and HU use (Yes vs. No) to compare the treatment effect of IMR-687 to placebo using the ITT population.

The van Elteren nonparametric test may be used for the evaluation of treatment difference across strata. The homogeneity of strata results for HU use and region will be investigated prior to the use of the stratified Wilcoxon test. If the data is homogeneous, we will perform the primary analysis stratifying for both region and HU use for the primary analysis and then for HU use only as supplementary analysis at the final analysis.

13.5.2.1 Derivation of Annualized Rate of VOCs

As described in Protocol Inclusion Criterion 3, a VOC is defined as a documented episode of acute painful crisis (for which there was not an explanation other than VOC) that involves moderate to severe pain lasting for at least 2 hours and at least one of the following:

- Use of escalated analgesia (including healthcare professional-instructed use of an analgesic prescription)
- A hospital, emergency department, or clinic visit and/or healthcare telephone consultation at the time of occurrence
- Diagnosis of acute chest syndrome (ACS) (defined as an acute illness characterized by fever and/or respiratory symptoms, accompanied by a new pulmonary infiltrate on a chest X-ray), hepatic sequestration, or splenic sequestration, or priapism (in males)

VOCs collected during the study are assumed to meet these criteria as well.

VOC information, including start and end date/time, primary setting for treatment (hospitalization/ emergency department, etc.), and treatments are collected on the "VOC" CRF page.

Annualized rate of VOCs is calculated as Total number of VOCs / ([Date of last dose of study drug– date of first dose of study drug + 1]/365.25).

Date of last dose of study drug is collected from the "End of Treatment" CRF page. If that date is not available (which is expected for some of the subjects in the IA), the data cut-off date will be used.

13.5.2.2 Primary Analysis of Primary Efficacy Endpoint

For the primary efficacy analysis, the following hypotheses (H_0 and H_a) will be tested first:

H_0 : The annualized rate of VOCs between IMR-687 highest tolerated dose and placebo = 0

H_a : The annualized rate of VOCs between IMR-687 highest tolerated dose and placebo \neq 0

If the above testing is successful, the following hypotheses (H_1 and H_b) will be tested:

H_1 : The annualized rate of VOCs between pooled IMR-687 and placebo = 0

H_b : The annualized rate of VOCs between IMR-687 pooled and placebo \neq 0

If the above testing is successful, the following hypotheses (H_2 and H_c) will be tested:

H_2 : The annualized rate of VOCs between IMR-687 lower dose and placebo = 0

H_c : The annualized rate of VOCs between IMR-687 lower dose and placebo \neq 0

A stratified Wilcoxon rank-sum test based on stratification factors of region (North America/Europe vs. Africa/Middle East) and HU use (Yes vs. No) will be used to compare the treatment effect of IMR-687 to placebo in the ITT analysis set and a two-sided p-value will be provided. The homogeneity of strata results will be investigated prior to conducting the primary analysis at the end of the study.

The primary endpoint comparison will be performed at both the IA and FA. The critical values for the significance are calculated based on a Lan-DeMets alpha spending function for IA (See [Section 12.2](#) for details), and the propagated alpha will be used for FA. If the two-sided p-value from the primary comparison is below the critical values for the significance in IA or FA (in favor of IMR-687 highest tolerated dose), the study is considered a success in terms of efficacy. If this boundary is crossed during the IA, the study may be unblinded and patients receiving placebo may be offered active treatment. See [Section 12.4](#) for details on the alpha control and hierarchical testing procedures.

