7.1.3. Open-Label Extension

Subjects who complete treatment (Week 52) in this study may be eligible to enroll in a planned open-label extension (OLE) study. The EOS safety follow-up visit (Week 56) will not be expected for subjects who directly roll over to the OLE study.

Figure 1: Study Design

Abbreviation: DMC = data monitoring committee.

* Prior to the introduction of IMR-687 higher dose, the DMC will review safety data for at least 5 subjects who received IMR-687. If the DMC recommends inclusion of the higher dose, randomization across 3 dose groups will then proceed as shown.

During study conduct under Protocol Version 3.0, the DMC approved the opening of enrollment in the higher dose IMR-687 group, which went into effect on 12 March 2021.

Table 1: Schedule of Assessments

	Screening Period	Baseline	Treatment Period													Follow-up Period		
			1	2	3	4	5	6	7	8	9	10	11	12	13	14		
Visit Number	1	2															16	
Study Week	-4 to 0	NA	1	2	4	6	8	12	16	20	24	30	36	44		ET/EOT	EOS	
Study Day	-28 to -1	1 ^a	7 ± 2	14 ± 3	28 ± 5	42 ± 5	56 ± 5	84 ± 5	112 ± 7	140 ± 7	168 ± 7	210 ± 7	252 ± 7	308 ± 7	364 ± 7		52 ^b	56
Administrative Procedures																	392 ± 7	
Informed consent	X																	
Demographic information	X																	
Medical/disease history	X																	
Inclusion/exclusion criteria ^b	X	X																
Randomization		X																
Telephone visits ^c				X		X												
Safety Assessments																		
Vital signs ^d	X	X	X		X		X	X	X	X	X	X	X	X	X	X	X	
Weight	X	X			X			X			X		X		X		X	
Height	X																X	
Physical examination ^e	X	X	X		X		X	X	X	X	X	X	X	X	X	X	X	
12-lead ECG ^f	X	X	X		X		X	X	X	X	X	X	X	X	X	X	X	
Hematology and serum chemistry	X	X	X		X		X	X	X	X	X	X	X	X	X	X	X	
Coagulation studies	X							X			X						X	
Urinalysis with urine creatinine, Pr:Cr ratio, and microalbumin	X	X	X		X		X	X	X	X	X	X	X	X	X			

Table 1: Schedule of Assessments (Continued)

	Screening Period	Baseline	Treatment Period													Follow-up Period		
			1	2	3	4	5	6	7	8	9	10	11	12	13	14		
Visit Number	1	2															16	
Study Week	-4 to 0	NA	1	2	4	6	8	12	16	20	24	30	36	44		ET/EOT	EOS	
Study Day	-28 to -1	1 ^a	7 ± 2	14 ± 3	28 ± 5	42 ± 5	56 ± 5	84 ± 5	112 ± 7	140 ± 7	168 ± 7	210 ± 7	252 ± 7	308 ± 7	364 ± 7		52 ^b	56
Serum pregnancy test ^g	X																	
Urine pregnancy test ^g		X	X		X		X	X	X	X	X	X	X	X	X	X	X	
Clinically indicated virology ^h	X																	
Adverse events ⁱ																	Continuous	

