8.4. Guidelines for Withdrawal of Subjects from Study Participation

Subjects will be informed that they withdraw from participation in the study at any time and for any reason, without prejudice to further medical care.

The investigator may also remove a subject from the study at their discretion if, in the investigator's opinion, it is not in the best interest of the subject to continue in the study.

If a subject must be withdrawn from study participation, the medical monitor should be informed and consulted regarding possible appropriate assessments to be completed in advance of study withdrawal. In case of withdrawal from the study, every effort will be made to complete both the early termination (ET) visit assessments and the EOS visit assessments, if possible. If a subject does not complete the ET assessments, every effort should be made to obtain the EOS assessments; in this case, the ET and EOS visits will coincide. If a final visit is not feasible, every effort to collect follow-up medical records will be attempted.

In the case of subjects who are lost to follow-up, the study site must attempt to contact the subject by phone, making at least 3 documented attempts, each at least 1 week apart. Additionally, a registered letter must have been sent with a copy on file. The study site should only deem the subject as lost to follow-up no less than 30 days following the first documented phone call attempt, unless circumstances preclude this (e.g., phone service has been discontinued or there is other evidence that contact is not feasible).

If the subject withdraws from the study, the specific circumstances surrounding the withdrawal must be recorded in the subject's eCRF.

Refer to Section [8.6](#) for details on subject replacement.

Justifiable reasons to discontinue a subject from treatment (Section [8.5](#)) and/or from the study may include, but are not limited to the following:

- The subject was erroneously included in the study (i.e., did not meet eligibility criteria)
- The subject experiences an SAE assessed as possibly or probably related to study drug
- The subject is unable to comply with the requirements of the protocol
- The subject participates in another investigational study
- The subject withdraws consent to participate in the study
- A subject for whom the blind is intentionally or accidentally broken

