10.2. Blinding

To ensure that the subject and site are blinded with respect to each subject's treatment assignment, placebo tablets and tablets for each dose level of IMR-687 are identical in appearance and are supplied in identical packaging. Each bottle will contain a code that identifies the contents as either 100 mg IMR-687, 150 mg IMR-687, 200 mg IMR-687, or placebo.

Every attempt should be made to preserve the integrity of study drug blinding. Except for cases of emergency unblinding, as described in Section 10.4, the randomization code will remain unbroken for subjects and study personnel at the site until the database has been locked. The blinded sponsor and contract research organization (CRO) study team members will be unblinded to the analysis results at the conclusion of the study (e.g., database lock).

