10.4. Emergency Unblinding

Unblinding is not always necessary to provide effective medical intervention and subject management in the event that a subject experiences a VOC, an SAE, or an event that results in cessation of treatment (see Section 8.7). However, in the exceptional circumstance in which the investigator believes that knowledge of the study drug assignment is essential to provide appropriate medical management, the treatment assignment for that subject will be provided to the investigator according to standard operating procedures at the CRO. The medical monitor and sponsor are available to the investigator as needed for any considerations of unblinding a

specific subject; however, the decision to unblind a specific subject relies solely on the clinical judgement of the investigator. That is, there is no requirement to discuss with the medical monitor and/or sponsor prior to unblinding a specific subject by the investigator; however, consultation is preferred. In the event that the investigator must unblind a subject and has not consulted with the medical monitor and/or sponsor, the investigator should notify the medical monitor and sponsor of the unblinding within 24 hours of breaking the blind.

After breaking the blind, the site staff should record the reason(s) for breaking the blind and any AEs leading to the breaking of the blind in the source documents and the appropriate eCRF pages. After breaking the blind, the subject will be discontinued from the study and should proceed with the ET and EOS visits according to the schedule of assessments ([Table 1](#)).

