6.0 Introduction

This SAP should be read in conjunction with the study protocol and case report form (CRF). Any further changes to the protocol or CRF may necessitate updates to the SAP prior to database lock. If the SAP and the final protocol are different, the SAP prevails.

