12.4 Final Analysis

The database will be locked prior to the final analysis (FA) which will be conducted when all randomized subjects have reached Week 56 or terminated early. As described in [Section 12.3](#), all the efficacy endpoints will be tested in a hierarchical order, at the highest tolerated dose of IMR-687 vs placebo. If all the efficacy comparisons are successful, testing of the IMR-687 pooled dose vs. placebo, and of lower dose vs. placebo will be performed. Propagated alpha from the primary efficacy analysis at the IA will be used in the FA to maintain an overall type I error rate of 5% for 2-sided testing. After the first instance of a failure to reject the null hypothesis, p-values from all remaining comparisons will still be reported, but deemed nominal. The hierarchical order of testing of primary, key secondary and other secondary endpoints is:

1. Annualized rate of VOCs
2. Time to first VOC
3. HbF responder rate at Week 24
4. Proportion of VOC-free subjects
5. Annualized rate of VOC-related hospitalization
6. Annualized rate of days hospitalized for VOC-related hospitalizations
7. Time to second VOC
8. Change from baseline in key biomarkers of RBC hemolysis (indirect bilirubin and % reticulocytes) at Week 24 and Week 52
9. HbF responder rate at Week 52
10. Change from baseline in HbF (%) and F-cells (%) at Week 24 and Week 52
11. Hb responder rates at Week 24 and Week 52
12. Change from baseline in total Hb (g/dL) at Week 24 and Week 52
13. Change from baseline in other biomarkers of RBC hemolysis (absolute reticulocytes and lactate dehydrogenase [LDH]) at Week 24 and Week 52
14. Change from baseline in biomarkers of adhesion such as soluble E-selectin (E-sel), P-selectin (P-sel), intercellular adhesion molecule 1 (ICAM-1), and vascular cell adhesion molecule 1 (VCAM-1) at Week 24 and Week 52
15. Change from baseline in biomarkers of inflammation such as high-sensitivity C-reactive protein (hsCRP) and myeloperoxidase (MPO) at Week 24 and Week 52
16. Change from baseline in biomarkers of cardiac stress such as N-terminal prohormone of brain natriuretic peptide (NT-proBNP) at Week 24 and Week 52
17. Change from baseline in RBC indices, such as mean corpuscular volume (MCV) at Week 24 and Week 52
18. Change from baseline in each measured subdomain of ASCQ-Me questionnaire at Week 24 and Week 52
19. Change from baseline in total preference score and individual domain scores of PROPr questionnaire at Week 24 and Week 52

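### The SAP allows unblinding and active drug for placebo subjects after interim success, the protocol has no provision for this, and the final analysis has no data cut if it happens

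*SAP*

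**What the plan says.** **Conduct after interim success.** SAP 13.5.2.2: "If this boundary is crossed during the IA, the study may be unblinded and patients receiving placebo may be offered active treatment".

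**Blinding.** Protocol 10.2 says that, emergency unblinding aside, "the randomization code will remain unbroken for subjects and study personnel at the site until the database has been locked". Protocol 10.3 opens the code for the interim only to certain sponsor representatives and designees. SAP 12.3 lets the blinded sponsor and CRO team see group results, not individual ones, once the interim is done.

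**Open-label drug.** Protocol 7.1.3 gives one route: "Subjects who complete treatment (Week 52) in this study may be eligible to enroll in a planned open-label extension (OLE) study".

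**Broken blind.** Protocol 8.4 lists, among justifiable reasons to discontinue, "A subject for whom the blind is intentionally or accidentally broken". Protocol 10.4, on emergency unblinding, says "After breaking the blind, the subject will be discontinued from the study". SAP Table 8 classes a broken blind as a missing-at-random reason for treatment discontinuation.

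**Precedence.** SAP 6.0: "If the SAP and the final protocol are different, the SAP prevails".

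**Final analysis.** SAP 12.4 runs when all randomised subjects have reached Week 56 or terminated early. It tests the hierarchy for the highest tolerated dose against placebo, including items such as "HbF responder rate at Week 52". SAP 11.4 analyses subjects by randomised arm. SAP 13.5.2.1 counts VOCs over the time from first to last dose of study drug, a term that Protocol 9.1 uses for both IMR-687 and placebo. SAP 13.5.3.1 censors time to first VOC at study end.

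**The concern.** The SAP clause allows something for which the protocol has no procedure: opening the study before lock and giving placebo subjects active drug. The precedence sentence favours the SAP, but it does not supply the missing procedure.

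The statistical consequence is separate. Suppose the clause is used, switched subjects stay in the study, and SAP 12.4 is then followed as written. Time on IMR-687 would be analysed as placebo time. VOCs reported open-label would be pooled with VOCs reported blind. A VOC depends on reported pain, escalated analgesia and contact with care, so knowledge of treatment can affect the count. These data would feed comparisons that the SAP treats as formal tests.

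**Working it through.** **1. The plan's own figures.** Inputs from SAP 8.1.2 and Appendix 7: 31 placebo, 49 higher dose, means 5.034 and 3, SD 2.7, two-sided alpha 0.05. A noncentral t calculation with n scaled by 3/π gives power 0.886 (SAP 0.880). For 24 and 37 it gives 0.788 (SAP 0.776). Lan-DeMets O'Brien-Fleming spending at 24/52 = 0.4615 gives one-sided 0.00097 at the interim and 0.0247 at the final, matching Table 5 after rounding.

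**2. How likely is the scenario?** The drift under the design effect is 2.034 / (2.7 × √(1/(31 × 0.955) + 1/(49 × 0.955))) = 3.21. The probability of p ≤ 0.002 is Φ(3.21 × √t − 3.09), where t is the share of full information.

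| t | probability |
|---|---|
| 0.46 | 18% |
| 0.70 | 34% |
| 1.00 | 55% |

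The SAP uses the first value of t. The others apply if early rates carry more information. The scenario is not remote.

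**3. Who is still on study?** SAP 8.1.1 gives 17 subjects randomised 2:1 and 98 randomised 1:2:1. SAP 8.0 dates the second phase from 12 March 2021, and accrual ended in August 2021. Placebo in the second phase is 98/4 = 24.5; in the first, 17/3 = 5.7; total 30.2 (SAP projection 31).

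If the last subject entered on 1 to 31 August 2021, Week 24 falls between 16 January and 15 February 2022. The second phase lasted 20.3 to 24.6 weeks, so its longest follow-up is then 44.3 to 48.6 weeks. None of its roughly 24 placebo subjects has reached Week 52.

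**4. Dilution.** Assume even accrual over a phase of A weeks, a full and immediate move from 5 to 3 VOCs a year, and no dropout. A subject who entered u weeks before the last one has 28 − lag − u weeks left, or none if that is negative. Dilution is 2.0 × (mean weeks left / 52) × (24.5/30.2). The 2:1 cohort adds less than 0.01 and is omitted.

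| Lag | Mean weeks left (A = 20.3; 24.6) | Dilution, VOC/year | Second-phase placebo subjects affected |
|---|---|---|---|
| none | 17.9; 15.7 | 0.56; 0.49 | 24.5; 24.5 |
| 90 days (12.9 weeks) | 5.7; 4.7 | 0.18; 0.15 | 18; 15 |

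With no lag, mean weeks left is 28 − A/2. With 90 days it is 15.14²/(2A), because subjects with u above 15.14 have finished.

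Some lag is certain. The SAP is dated 1 March 2022, which is 14 to 44 days after the Week 24 dates above, and SAP 12.0 requires locked, cleaned data.

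**5. Which results are exposed?**
- Not exposed: interim success on the primary, which SAP 12.3 allows to be claimed at that point, and every Week 24 endpoint, since the interim follows all Week 24 visits.
- Little exposed: time to first VOC. At 5 and 3 VOCs a year with Poisson events, 1 − exp(−5 × 24/52) = 90% and 1 − exp(−3 × 24/52) = 75% have had an event by Week 24.
- Exposed: Week 52 secondary endpoints (final hierarchy item 8 onward), VOC-related rates, late time-to-event data, and the final estimate of the primary.

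**6. A related inconsistency.** SAP 12.3 repeats the primary test at the final analysis only if the interim fails. SAP 13.5.2.2 says that it is performed at both.

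**The case against.** The clause is permissive on both unblinding and active drug, and it does not say when, where or under which protocol the drug would be given. An in-study switch would need a protocol amendment with regulatory and ethics approval (Protocol 15.1.1). SAP 6.0 foresees SAP updates before lock, and details of interim unblinding sit in a plan outside these documents. As-randomised analysis is also a legitimate strategy, and dilution works against the drug. All of this stands. It makes the problem conditional, but it does not supply the missing rule, and a rule written after interim results are known would look data-driven.

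Three stronger readings are tempting.
- A reader might infer that Protocol 10.4 requires every unblinded subject to leave the study, so that the clause contradicts it directly. That section covers emergency unblinding by an investigator. Protocol 8.4 only lists a broken blind as a possible reason. If a switch were handled as a discontinuation, the VOC rate would stop at last dose and Table 8 would apply, but neither document says that it is handled so.
- A reader might infer that the whole final analysis, or the interim success itself, is compromised. Step 5 shows otherwise.
- A reader might spread accrual evenly from August 2020 to August 2021. The phase counts and the March 2021 date rule that out.

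**Conclusion.** The concern holds in conditional form. SAP 13.5.2.2 does not fit Protocol 10.2, Protocol 7.1.3 or SAP 12.3, and the passages must be reconciled. If the clause is used and switched subjects remain in follow-up, the final analysis as written would count open-label and active-drug data as placebo data in formally tested comparisons.

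The loss is about 0.5 VOC a year from a planned difference of 2.0 if the switch is immediate, and about 0.15 after 90 days. Both figures rest on even accrual within the 1:2:1 phase, every eligible placebo subject switching, no dropout, and a full, immediate drug effect. A partial uptake or slower effect would give less. Reporting bias after unblinding is additional and cannot be sized from the documents.

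**What to change.** 1. Reconcile SAP 13.5.2.2 with Protocol 7.1.3, 8.4 and 10.2 and with SAP 12.3. State whether a post-interim switch counts as a discontinuation. The conduct rule is the sponsor's decision.
2. Before interim results are known, add to SAP 12.4: if subjects are unblinded or switched after the interim, confirmatory final efficacy comparisons use data only up to each subject's unblinding or switch date. VOC counts and exposure are truncated there, time-to-event endpoints are censored there, and later laboratory and quality-of-life values are excluded. As-randomised results on all data are supportive.
3. State that Week 52 responder tests are descriptive if they would then rest mainly on Week 36 values carried forward. SAP 13.5.4 fills a missing Week 52 HbF value from Week 36 and applies the same approach to Hb, so a cut alone would turn many Week 52 responder results into Week 36 results.
4. Reconcile SAP 12.3 with 13.5.2.2 on whether the primary is tested again at the final analysis after interim success.

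The cost is SAP wording and a protocol clarification. The downside is fewer confirmatory Week 52 comparisons, and only if the clause is used.

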13.5.2.3 Missing Value Consideration for the Primary Efficacy Analysis

The value of the primary endpoint, annualized rate of VOCs, will be non-missing by definition. However, subjects included in the ITT analysis may not all complete the 52-week treatment period. In the context of this endpoint, the unobserved VOC events after treatment discontinuation will be considered missing values. This calculation accounts for early treatment discontinuation by extrapolating the VOC rate annualized to one year. The primary analysis assumes the unobserved rate of VOC will be the same for the observed rate for the same subject.

Missing data will not be imputed for primary endpoint analysis methods. Data imputation strategies will be employed for sensitivity analysis.

Understanding the reasons why data are missing is important to correctly interpret and handle the observed data. If the missing data mechanism is independent of missing outcome values, conditional on earlier observed outcome variables and/or covariates, the outcome values are missing at random (MAR). If the probability of missingness depends on an outside variable not in the model or is related to unobserved outcome values at the time of dropout and possibly afterward then the values are missing not at random (MNAR).

Table 8 summarizes the classification with the potential reasons. The missing data pattern will be summarized and the impact of these missing values will be explored in the sensitivity analysis below.

Table 8 Classification of Missing Data Pattern

| Missing Data Pattern | Reason for Treatment Discontinuation |
|------------------------------|---|
| MNAR (Missing Not at Random) | 
Due to efficacy/safety related reasons:
 
 • Adverse Event • Death • Lack of Efficacy • Lost to Follow-up • Non-Compliance with Study Protocol • Non-Compliance with Study Drug • Physician Decision • Study Terminated by Sponsor • Subject Participation in Another Investigational Study • Trial Site Terminated by Sponsor • Withdrawal of Consent • Other (efficacy/safety related) |
| MAR (Missing at Random) | 
Due to non-efficacy/non-safety related reasons:
 
 • Pregnancy • Study Blind Intentionally or Accidentally Broken • Subject Erroneously Included in Study (i.e. did not meet eligibility criteria) • COVID-19 • Other (not efficacy/safety related) |

